Approach: *We will randomize 20 clinics to receive the ATP or no intervention (SOC) and compare disclosure and appropriate transition using pre-specified milestones among a group of children and adolescents with heterogeneous ages. During early implementation, we will monitor fidelity to the intervention using modified plan-do-study-act (PDSA) cycles. We will track implementation outcomes and factors influencing implementation during the initial ATP implementation phase (6 months). During this time, the study team will discuss and support changes to refine the tool as needed at each facility. Following the initial implementation period, HCWs will take part in focus group discussions to share their suggestions for optimizing the transition tool based on their experience. Understanding personal experiences with the tool will provide an opportunity for lessons learned and continued refinement of the intervention. At the end of the study, we will qualitatively evaluate acceptability, appropriateness and feasibility of the ATP by conducting interviews and FGDs with all HCWs from implementing sites and adolescents from a sub-set of intervention sites, purposively selecting to include participants from high and low performing facilities. We will also conduct pre-trial and post-trial surveys with adolescents and HCWs to quantitatively assess acceptability, appropriateness, feasibility of the ATP and implementation intervention fidelity. At 6-monthly intervals, we will collect readiness assessment information from adolescents in participating clinics.*

SECTION 3: STUDY OUTCOMES

Aim 1

- Prevalence of transition
- Age at transition
- Co-factors for retention
- Age at disclosure
- Co-factors of disclosure
- Individual level co-factors of effective transition
- Facility level co-factors of effective transition

Aim 2

- Adapted transition tool

Aim 3

- The primary outcome is **disclosure** among non-disclosed adolescents and **effective transition and transition readiness** among disclosed adolescents

- Disclosure will be defined as no, partial or complete disclosure. Time to disclosure and age at disclosure will also be assessed.
- Effective transition with retention in care will be defined as completing a visit on the adult day or completing a visit without a caregiver and repeat visits continuing for at least 6 months after transition.
- Transition readiness will be defined as change in response to readiness assessment questions administered every 6 months

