Aim 3: We will enroll 20 clinics located in Nairobi, Homabay, Kajiado and Nakuru counties. Adolescents and HCWs in intervention sites will participate in post-trial interviews, HCWs from intervention sites will participate in pre and post-trial surveys, PDSA cycles and FGDs, and a sample of adolescents in all sites will participate in pre and post-trial surveys. Caregivers of children and young adults who have not yet reached disclosure, as well as fully disclosed adolescents and young adults, will also participate in 6-monthly readiness assessment surveys.

5b. Study population

AIM 1:

Facility Survey: Stratified random sampling will be used to select up to 102 clinics based on clinic volume. The sampling frame of all national facilities currently using EMR will be utilized in this approach. We will exclude clinics with less than 300 patients in HIV care, given that the number of adolescents attending the clinic would be small and hard to evaluate, and divide the remaining clinics equally into tertiles. The tertiles will represent the small, medium, and large clinic sizes. Within each stratum, the clinics will be chosen using equal probability sampling and we will select 34 clinics per stratum. One or two designees per facility will be enrolled to complete the facility survey.

Retrospective Records Review: The study will include extraction of routinely collected health records of up to 15,000 adolescents aged 10-24, currently engaged in HIV care in Kenya and attending the facilities included in the facility survey.

AIM 2:

Adaptation Interviews (Table 2): We will conduct 16 focus group discussions with HIV infected adolescents aged 14-24 years, 8 focus group discussions with caregivers of HIV infected adolescents aged 14-24 years, 38 interviews with HCWs providing pediatric and adolescent HIV care, and 30 hospital administrators and policy makers identified by national and local health administration offices. We will recruit adolescents, primary caregivers and HCWs from KNH and 6-10 facilities that participated in Aim 1.

Working Group Meeting: For this aim of the study, we will enroll approximately 40 HCWs from clinics throughout Kenya providing HIV care for adolescents.

Table 2: Purposive sampling scheme and data collection details for Aim 2

Focus Groups and Interviews to DEVELOP										Working Group to ADAPT/REVISE	

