An individual who meets any of the following criteria will be excluded from participation in this study: Conditions that would place the individual at increased risk or preclude the individual's full compliance with or completion of the study.

Table 4. Inclusion Criteria for all participants/clinics

	Population	Sampling	N	Inclusion Criteria
AIM 1: Program data abstraction				
Facility Survey Site	HIV care clinics	Selected randomly from clinics with EMR systems in place and >300 patients in HIV care	102	EMR system in place >300 patients in HIV care
Facility Survey Designee	HCW	Selected as representative for clinic to complete facility survey; will enroll 1-2 HCWs to help complete the survey per study site	102 sites	≥18 years of age Employed at facility in clinical care for at least 6 months and/or have a 1 year contract (i.e. not temporary staff) Provides clinical services to adolescents
Retrospective Records Review	Adolescents ages 10-24	All adolescents from the 102 selected facilities	Up to 15,000	-Aged 10-24 years of age -Attended clinic ≥1 time after January 1, 2016 -Attended clinic included in facility survey
Aim 2: ADAPT and OPTIMIZE				
Working Group	HCWs	Purposively selected from HCWs providing adolescent care	40 for Working Group	-≥18 years of age -Employed at clinic in Kenya -Employed in clinical care for at least 6 months and/or have a 1 year contract (i.e. not temporary staff) -Provides clinical services to adolescents
Adaptation IDI and FGDs	Adolescents (aged 14-24 years)	Adolescents in HIV care (8 FGDs for adolescents who have not completed transition, 8 FGDs for adolescents who have completed transition)	16 FGDs and 96 adolescents total (from clinics with different models of care)	-Ages 14-24 -Seeking treatment services at facilities assessed in Aim 1 -Knows that they have HIV -Attended clinic for at least 1 year
	Caregivers of HIV-infected adolescents aged 14-24 years	Caregivers of adolescents who have and have not completed transition	8 FGDs and 48 caregivers total (from clinics with different models of care)	-≥18 years of age -Seeking treatment services at facilities assessed in Aim 1 -Caregiver of adolescent age 14-24 years seeking treatment at selected site -Adolescent has attended clinics for at least 1 year

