For each clinic that agrees to participate, routine clinic data will be abstracted from the EMR system and from paper forms when EMR systems are not available. The medical records collected from the patient charts will include data tracking routine services offered and laboratory measurements collected. EMR or other medical record data will be abstracted directly from clinics or from implementing partners, whichever is most convenient for the clinic. If data staff at the partner organization or at the clinic are unable to extract the data on their own, hired technicians or study staff will travel to sites and assist with data abstraction directly. All medical records for adolescents ages 10-24 attending the clinic at least 1 time between January 1, 2016 and the date of data abstraction (but not later than December 31, 2017) will be pulled.

Data Collection Procedures:

For EMR data, data will be extracted by running a standardized query of the EMR database. The query will pull serial records for all adolescents ages 10-24 years who have at least 1 visit on or following January 1, 2016 and attend a clinic selected to participate in the facility survey. This will include all data on each adolescent from January 1, 2016 up until the date when data is abstracted but not later than December 31, 2017. We will not obtain individual consent for pulling adolescent records from the EMR. We will obtain a waiver of consent to obtain this information. Data collected will obtain basic demographic and HIV-specific clinical care outcomes as detailed in the attached file listing variables to be collected. This information is already charted as part of routine care. For paper records, data will be abstracted using Case

Report Forms (CRFs) and Open Data Kit (ODK) or REDCap. We will abstract selected variables from the EMR and paper based records including: client age at enrollment, caregiver type, sex, date/age of HIV diagnosis, CD4 count or percent, date of ART initiation, attendance at pediatric or adult clinic day (data obtained from facility survey and calculated by visit dates), and presence of caregiver at the visit (in EMR counseling notes). Serial data will be obtained on follow-up at the clinic. A list of variables that will be collected is attached.

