A total of up to 60 providers will be selected from among all providers at intervention facilities, including 10 IDIs with ATTACH study staff. HCWs will be purposively selected to represent different cadres of HCWs who provide services for adolescents and are directly involved in implementation of the ATP. We believe that 5 providers per site (50 total), and 10 ATTACH study nurses, will give us adequate numbers to attain saturation during data collection and enough diversity in health provider cadre to ensure different perspectives are accurately represented.

A total of up to 96 adolescents will be selected for interviews. We will purposively select adolescents with a range of ages and intervention exposure. Clinic providers will assist in identifying and referring adolescents who are aware of their HIV status and have been through disclosure as well as adolescents who have been exposed to the ATP. Eligibility of adolescents will be confirmed by reviewing their chart for documentation of disclosure and transition intervention exposure. We believe that 6-10 adolescents from each site (96 total) will give us adequate numbers to attain saturation during data collection and will provide enough diversity in experiences to ensure different perspectives are accurately represented.

11b. Overview of analysis plan

Aim 1

Follow-up at 6-month post-enrollment and annually thereafter will be determined and summarized as proportion retained for given interval (e.g., 6-month retention, 12-month retention, 36-month retention) with anticipated denominator in follow-up based on enrollment date. Cofactors for loss to follow-up will be determined using Cox regression. Potential cofactors of loss to follow-up include age at enrollment, CD4, caregiver type (biologic, mother or father), age at HIV diagnosis, sex, illness or hospitalization, and evidence of transition. Proportion with evidence of transition and mean/median age of transition will be computed. Cofactors of transition will be determined including child/adolescent age, age at HIV diagnosis, evidence of disclosure, caregiver type using logistic regression. Post-transition retention will be determined and cofactors of effective transition (documented 6-month or longer follow-up after transition) will be assessed using logistic regression.

Aim 2

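### Aim 1 counts retention from enrolment out to 36 months among adolescents selected for a visit since January 2016, with no rule for delayed entry

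*Combined protocol and SAP*

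**What the plan says.** All references are to the protocol; the SAP covers only the trial.

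- **Outcome and time scale.** Section 11b, Aim 1, determines follow-up at 6 months after enrolment and then yearly, "summarized as proportion retained for given interval (e.g., 6-month retention, 12-month retention, 36-month retention"), "with anticipated denominator in follow-up based on enrollment date".
- **Model.** The same paragraph states: "Cofactors for loss to follow-up will be determined using Cox regression". It continues: "Potential cofactors of loss to follow-up include age at enrollment", followed by other factors. Section 3 lists "Co-factors for retention" among the Aim 1 outcomes.
- **Who is included.** Section 5b describes the records as those of "adolescents aged 10-24, currently engaged in HIV care in Kenya". Table 4 requires "Attended clinic ≥1 time after January 1, 2016". The query in section 7a pulls adolescents "who have at least 1 visit on or following January 1, 2016". Section 11a repeats the visit rule. None of these rules restricts enrolment date.
- **What data are held.** Section 7a limits the pull to 1 January 2016 up to abstraction, and no later than 31 December 2017. Section 10 gives the same Aim 1 window, but its examples of data include visits going back to enrolment.
- **Cohort and age.** The precision text in section 11a describes 5,000 adolescents enrolled in care over the preceding 12 to 24 months. Section 11a also gives the analysed ages as 10-19, where Table 4 and sections 5b and 7a give 10-24.

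Delayed entry, left truncation, the Cox time origin and an Aim 1 definition of loss to follow-up are not stated.

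**The concern.** Retention after enrolment asks what share of those who enrolled are still in care some months later. It needs everyone who enrolled, including those who left early. Here a record enters the dataset only if the adolescent attended in 2016 or later. For someone who enrolled years before, that visit is itself evidence of having been retained. An enrolment-date denominator removes people who enrolled too recently, but it cannot restore people whose records were never pulled.

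Two results are at stake: the long-interval retention figures, which may be taken as benchmarks for adolescent programmes, and the cofactor analysis. In a cohort defined by age in 2016-2017, a younger age at enrolment tends to mean an earlier enrolment, and hence a longer stretch in which loss could not have been recorded. That can make younger enrolment look protective when it is not.

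**Working it through.** **1. The plan's own Aim 1 figure.** Inputs from section 11a: prevalence 60%, precision 2.5 points, 95% confidence, ICC 0.05, 50 adolescents per clinic.

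- Simple random sample: 1.96² × 0.6 × 0.4 / 0.025² = 1,475.1
- Design effect: 1 + 49 × 0.05 = 3.45
- Clinics: 1,475.1 × 3.45 / 50 = 101.8, so 102

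This reproduces, as do the Table 7 half-widths. They describe random error only and are not in dispute.

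**2. The calendar, from the documents' dates alone.**

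| Enrolled | Consequence of the inclusion rule |
|---|---|
| Before 1 January 2013 | Qualifying visit falls at or after month 36 |
| 2013-2014 | Can reach month 36, but must have attended at least 12 months after enrolment |
| 2015 | Cannot reach month 36; must still be attending in 2016 or later |
| From 1 January 2016 | No selection, but at most 24 months of follow-up |

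So no unselected adolescent can contribute to a 36-month figure.

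**3. Illustrative size.** Assumptions, none given for Aim 1:

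- 24-month loss of 20% or 25%, borrowed from the Aim 3 control-arm figures in Table 8
- constant hazard
- uniform enrolment starting between 2006 and 2014
- earlier visits held, or earlier retention inferred
- nobody lost before 2016 returns.

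Let S24 be 24-month retention, λ = −ln(S24)/2 per year, u the enrolment date and a = 2016 − u. A person is included if still in care at time a. Then

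apparent 36-month retention = ∫exp(−λ·max(3, a))du / ∫exp(−λa)du, with u from the start date to 2015.

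*Smallest case (2014 start, 20% loss).* λ = 0.1116 and a runs from 1 to 2.
- True: exp(−3λ) = 0.7155
- Mean inclusion probability: (0.8944 − 0.8000)/0.1116 = 0.846
- Apparent: 0.7155/0.846 = 0.845, about 13 points high

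*Largest case (2006 start, 25% loss).* λ = 0.1438 and a runs from 1 to 10.
- True: 0.6495
- Numerator: 2 × 0.6495 + (0.6495 − 0.2373)/0.1438 = 4.165
- Denominator: (0.8660 − 0.2373)/0.1438 = 4.371
- Apparent: 4.165/4.371 = 0.953, about 30 points high

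For k = 0.5, 1 or 2 years, replace 3 by k, end enrolment at 2018 − k, and set a = 0 for enrolment from 2016. The last column lets 20% of those lost before 2016 return, coded as not retained.

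| Interval | Upward bias, no returners (points) | With 20% returners (points) |
|---|---|---|
| 6 months | 2.5-5.2 | 2.0-3.6 |
| 12 months | 5-10 | 4-7 |
| 24 months | 9-21 | 7-14 |
| 36 months | 13-30 | 10-20 |

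For those enrolled from 1 January 2016, the bias at 6 and 12 months is zero.

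**4. Cox model.** Simulation with 24-month loss of 20%, age on 1 January 2016 uniform and independent of enrolment date, no true age effect, and time from enrolment without delayed entry. The hazard ratio per 5 years of age at enrolment is about 1.1 (2014 start) to 1.8 (2006 start) for ages 10-24, and about 1.2 to 2.9 for ages 10-19. With delayed entry at 1 January 2016 it returns to about 1.0.

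**5. Does delayed entry repair the retention curve?** Simulated Kaplan-Meier at 36 months (2010 start, 20% loss, true value 0.716) gives 0.885 without delayed entry and 0.716 with entry at 1 January 2016. Entry at the first visit from that date is also unbiased when loss is dated at the last visit. When loss is dated 6 months after the last visit, it gives 0.77-0.79 against 0.735 under that same definition, because the qualifying visit guarantees some event-free time.

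**The case against.** The strongest reply is that section 11b is an overview and 36 months is only an example. Aim 1 is formative and descriptive, and the variable list sits in an attachment that may settle which visits are held. The literal text of sections 7a and 10 limits Aim 1 records to 2016-2017. On that text the result is not an inflated 36-month figure but one that cannot be observed, and the upward-bias figures require going beyond it. The mention in section 10 of visits back to enrolment is one example in an item that serves both Aim 1 and Aim 3, so it is weak evidence that older visits are held. The section 11a wording on the preceding 12 to 24 months can also be read as a recent-enrollee cohort, in which selection at 6 and 12 months would be small or absent.

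Much of this stands, and it limits the claim: direction and size depend on which records are held. It does not clear the plan. On the recent-enrollee reading 36 months is still unobservable, and Table 4 and sections 7a and 11a set no such enrolment limit. Yearly retention from enrolment is the stated method, not just the example. Section 14 names only the representativeness of EMR clinics as an Aim 1 limitation.

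A reader might infer that every Aim 1 retention figure is biased, or that the sample size fails. Neither follows. The 6- and 12-month figures for those enrolled from 2016 are sound, and retention within 2016-2017 can properly use a visit in the window as its denominator. Nor do the documents support a downward bias: that would need months without held visits to be scored as not retained, a rule stated nowhere.

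**Conclusion.** The point holds for Aim 1 retention counted from enrolment, and for its Cox model if that is timed from enrolment without delayed entry. As written, the 36-month figure is either conditional on later attendance or not observable, and it cannot be read as retention after enrolment. That conclusion rests on the documents' dates alone.

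The sizes do not. The 13 to 30 points and the hazard ratios of about 1.1-1.8 (ages 10-24) or 1.2-2.9 (ages 10-19) rest on a borrowed loss rate and an assumed enrolment pattern. They show that the problem can be large, not how large it is here. The Cox result is also conditional, since the plan states no time origin.

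It would be wrong to carry this over to the cluster trial: Aim 3, its power, Table 7 and the 102-clinic calculation are unaffected. It should be fixed because the remedy is cheap and the figure would otherwise mislead.

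**What to change.** State for Aim 1 the time origin, the rule for entry to the risk set and a dated definition of loss to follow-up, including how adolescents who lapsed before 2016 and returned are coded. Then choose one:

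- **(a) Delayed entry.** Use left-truncated Kaplan-Meier and Cox. Pre-2016 enrollees enter at their first visit from 1 January 2016 and later enrollees at enrolment, with loss dated at the last visit. If loss is dated after a grace period, set entry so that the guaranteed event-free time after the qualifying visit is not counted. This needs only enrolment date and 2016-2017 visits.
- **(b) Restriction.** Report enrolment-based 6- and 12-month retention only for those enrolled from 1 January 2016. Drop 36-month retention, or label it as conditional on attendance in 2016-2017.

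Confirm that enrolment date is in the abstraction list; section 7a names age at enrolment, not the date. Reconcile Table 4 and sections 5b, 7a, 10 and 11a on the visits held, the age range and the cohort.

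**Cost.** Under (a), early follow-up rests mainly on recent enrollees, so intervals widen. Under (b), fewer adolescents contribute and there is no unconditional 36-month figure. Section 8 places Aim 1 in year 1 with dissemination in year 2, so if it has already been analysed the cost is re-analysis or relabelling.

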As many HIV-infected children on ART survive to adulthood in sub-Saharan Africa, improving systems for disclosure and transition to adult care is a high priority. There is need for better data on transition in high volume HIV clinics in Africa, and these clinics require feasible, effective systematic approaches to improve disclosure and transition. A disclosure tool used in Namibia demonstrates effectiveness and acceptability and could be adapted for use in other settings. In addition, the Got Transition model, which was developed following broad expert consensus and programmatic evaluation in US settings, has a clear framework and useful resources relevant to pediatric HIV transition in Africa. Combining these interventions using an implementation science

approach (program evaluation, adaptation and a cluster RCT) has potential to provide high quality evidence for broader use of these approaches and to improve long-term outcomes for adolescents with HIV.

SECTION 2: OBJECTIVES

2a. Study Objective

This study aims to evaluate rates and co-factors of effective transition in HIV treatment programs in Kenya and to adapt, implement, and evaluate an Adolescent Transition Package (ATP) that combines an adapted US-based transition tool and a disclosure tool associated with improved disclosure outcomes in Namibia.

2b. Specific Objectives

Aim 1: To use programmatic data (KenyaEMR and paper files) to estimate prevalence of transition and disclosure, age at transition and disclosure, and individual-level co-factors of effective transition from pediatric to adult HIV care and retention and HIV disclosure among 10-24 year olds. To determine transition practices in Kenyan clinics using a facility survey.

Effective transition will be defined as enrollment into adult care within 6 months of exiting the pediatric care and continued clinical follow-up for at least 6 months thereafter, as evidenced by a second clinic visit recorded in the EMR.

Hypothesis: Transition will occur at varied ages (median 18 years); effective transition and earlier transition age will be associated with the presence of a transition plan and adolescent friendly services at the facility, later age at child HIV diagnosis, earlier age of HIV disclosure, parent on ART, better health status of the child at enrollment into HIV care and at transfer (CD4, WHO stage, viral load), pregnancy or marital status of the adolescent, and evidence of consistent adherence and retention prior to transition.

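### If transition is coded ever/never from enrollment in the Aim 1 Cox model for loss to follow-up, immortal time biases its hazard ratio towards protection; 11b should fix the time origin, entry time and covariate timing

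*Combined protocol and SAP*

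**What the plan says.** Section 11b, Aim 1, first summarises retention at 6 months, 12 months and later intervals, "with anticipated denominator in follow-up based on enrollment date". It then states: "Cofactors for loss to follow-up will be determined using Cox regression". The candidate list follows: "Potential cofactors of loss to follow-up include age at enrollment, CD4, caregiver type", then age at HIV diagnosis, sex, and finally "illness or hospitalization, and evidence of transition". The next sentence plans the proportion of youth with evidence of transition, and the one after that models transition by logistic regression.

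Section 2b places transition after a spell in pediatric care: "Effective transition will be defined as enrollment into adult care within 6 months of exiting the pediatric care". Its hypothesis mentions "better health status of the child at enrollment into HIV care and at transfer (CD4, WHO stage, viral load"), but for cofactors of transition, not for this model.

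Section 7a restricts the extraction to youth aged 10-24 with at least one visit on or after 1 January 2016, and to data from that date to 31 December 2017 at the latest. It also says "Serial data will be obtained on follow-up at the clinic", with pediatric or adult clinic day worked out from visit dates.

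The SAP covers only the cluster trial and adds nothing on this model.

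**The concern.** A youth can show evidence of transition only if still in care when it happens. Someone lost early is therefore always counted as not transitioned, while a transitioned youth brings to that group all the time before transition, when a loss could not have been counted against it. This is immortal time. It lowers the hazard ratio for transition whatever the real effect.

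Section 11b names no time-updated covariate, start-stop interval or landmark. It uses the same term, evidence of transition, for a per-person proportion in the next sentence. An analyst following the text would most naturally enter a yes/no variable fixed from enrollment.

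Cofactors of retention are a listed Aim 1 outcome (section 3), and the literature review (1b) raises the possibility that poor transition contributes to poor adolescent outcomes. A hazard ratio on the wrong side of 1 would mislead on that question.

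**Working it through.** **The plan's own figure.** The documents give no event count, hazard ratio or power for this model, so there is nothing to reproduce. The Aim 1 sample size is a separate precision calculation and is sound: 1.96² × 0.6 × 0.4 / 0.025² = 1475; × (1 + 49 × 0.05) = × 3.45 gives 5089; / 50 gives 102 clinics.

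**Inputs.** Aim 1 states no rates, so these are borrowed from Aim 3 planning in section 11a and are assumptions here:
- Transition in 24 months: 20% (control-arm expectation); 10% to 50% tried.
- Loss in 24 months: 25% and 15% (Table 8, age 16-24, control and intervention columns).

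**Rough size by hand.** If transition times spread evenly over 24 months, a transitioned youth is truly exposed for about 12 of the 24 months credited. The loss rate is diluted by about 12/24 = 0.5, so a null effect appears as a hazard ratio near 0.5.

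**Simulation.** Exponential times to loss and transition. Monthly hazards are −ln(1 − 0.25)/24 = 0.0120 for loss and −ln(1 − 0.20)/24 = 0.0093 for transition in the base case. Clinic clustering and delayed entry were ignored at this step. Cox models were fitted with transition as ever/never from enrollment and as time-updated.

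| True hazard ratio | Ever/never coding | Time-updated coding |
|---|---|---|
| 1.0 | 0.39-0.48 | 0.98-1.03 |
| 1.5 | 0.57-0.72 | 1.49-1.53 |
| 2.0 | 0.75-0.94 | 1.99-2.02 |
| 3.0 | 1.09-1.38 | 2.99-3.04 |

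In the base case with no true effect, ever/never coding gave 0.47. With 5000 youth it was significantly protective in all 300 runs (typical 95% interval 0.38 to 0.55); time-updated coding rejected in about 6%.

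**Effect of the data window.** Section 11b gives 36-month retention as an example. With data ending by 31 December 2017, that requires enrollment by 31 December 2014, before the window opens. Youth enrolled before 2016 enter the sample only if still in care in 2016, so their earlier time is also event-free by selection. If transitions are recorded only inside the window, all that time counts as not transitioned, and the bias turns round.

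A null simulation used enrollment from 8 years before to 2 years into a 2-year window, loss hazard 0.08-0.144 per year and transition hazard 0.11-0.30 per year. Time-updated coding without delayed entry gave hazard ratios of about 1.9 to 2.2. Adding delayed entry brought them to between 0.89 and 1.02 over the runs made. The size of the reversal depends on how enrollment and transition times are spread; its direction follows from the selection.

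**CD4 and hospitalization.** Section 11b dates neither. For youth enrolled before 2016, values arising inside the window fall after enrollment, but a stored enrollment CD4 may exist. No size was computed for either.

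**The case against.** Section 11b is headed as an overview, Cox regression accepts time-updated covariates, and section 7a collects the dated visits they need. Nothing says that transition will be fixed. The enrollment origin is stated for the retention proportions and only inferred for the Cox model. All of this is correct, so the bias is conditional on the coding. The condition is nonetheless the natural reading, and no other text rules it out.

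A reader might infer three stronger things that the documents do not support:
- That transition must look protective by construction. This needs fixed coding, and even then a true hazard ratio of 3 still appears above 1.
- That CD4 and hospitalization are known to be sampled after the clock starts. They are undated and could be enrollment values.
- That the case for the intervention rests on this estimate. Transition is one of several potential cofactors, post-transition retention is planned separately, and the package is judged in the cluster trial.

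It is also fair to object that time-updating alone is not a sufficient repair. The data-window calculation bears this out.

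**Conclusion.** The point holds conditionally. If evidence of transition is entered as ever/never from enrollment, its hazard ratio is biased towards protection. With no true effect it is about 0.39 to 0.48 under the borrowed Aim 3 rates and about 0.3 to 0.5 over other assumed rates. True harm of 1.5 or 2.0 would appear as benefit; harm of 3.0 would still show, though attenuated.

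These sizes rest on rates that Aim 1 does not state, on transition being unrelated to the underlying risk of loss, and on transitions being recorded. The bias would be weaker if many transitions before 2016 went unrecorded and those youth were counted as not transitioned.

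For CD4 and hospitalization the finding is unspecified timing only. The trial's primary outcome and its power are unaffected.

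**What to change.** In section 11b, Aim 1:
- State enrollment as the time origin of the Cox model.
- Enter transition as a time-updated covariate that switches on at its first recorded date.
- Use delayed entry (left truncation) at the later of enrollment and 1 January 2016.
- Enter illness or hospitalization recorded after entry as time-updated.
- Take CD4 either at enrollment, within a fixed window, or as the latest value, time-updated.

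The cost is a few sentences and some extra data preparation to split person-time, using serial visit data already planned. One limit remains: transitions before 2016 may not be datable, so the plan should say how those youth are classified. Section 8 places Aim 1 early in the study; if the model has already been fitted, the change is a re-run before the hazard ratio for transition is relied on.
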